3.6.2 Statistical Methods for Safety Analyses

Safety and tolerability will be assessed by clinical review of all relevant parameters, including AEs, ECG, laboratory tests, and vital signs.

The safety analysis will follow a tiered approach (Table 4). The tiers differ with respect to the analyses that will be performed. AEs (specific terms as well as system organ class terms) and events that meet predefined limits of change in laboratory and vital signs parameters are either pre-specified as Tier-1 endpoints, or will be classified as belong to "Tier 2" or "Tier 3", based on the number of events observed.

Tier 1 Events

Safety parameters or adverse events of special interest that are identified a priori constitute Tier 1 safety endpoints that will be subject to inferential testing for statistical significance.

There are no known AEs associated with participants with RCC for which determination of a p-value is expected to impact the safety assessment. Therefore, there are no Tier 1 events for this protocol.

Tier 2 Events

Tier 2 parameters will be assessed via point estimates with 95% CIs provided for differences in the proportion of participants with events using the Miettinen and Nurminen method, an unconditional, asymptotic method [1].

Membership in Tier 2 requires that at least 10% of participants in any treatment group exhibit the event; all other AEs and predefined limits of change will belong to Tier 3. The threshold of at least 10% of participants was chosen for Tier 2 events because the population enrolled in this study is in critical condition and usually experiences various AEs of similar types regardless of treatment; events reported less frequently than 10% of participants would obscure the assessment of the overall safety profile and add little to the interpretation of potentially meaningful treatment differences. In addition, Grade 3 to 5 AEs (\geq 5% of participants in 1 of the treatment groups) and SAEs (\geq 5% of participants in 1 of the treatment

groups) will be considered Tier 2 endpoints. Because many 95% CIs may be provided without adjustment for multiplicity, the CIs should be regarded as a helpful descriptive measure to be used in safety review, not as a formal method for assessing the statistical significance of the between-group differences.

Tier 3 Events

Safety endpoints that are not Tier 1 or 2 events are considered Tier 3 events. Only point estimates by treatment group are provided for Tier 3 safety parameters.

Continuous Safety Measures

Continuous measures such as changes from baseline in laboratory parameters, summary statistics for baseline, on-treatment, and change from baseline values will be provided by treatment group in table format.

Statistics

Х

Х

Х

Х

95% CI for Safety Descriptive Safety Endpoint Treatment Tier Comparison Any AE ($\geq 10\%$ of participants in one of the Х treatment groups) Any serious AE (\geq 5% of participants in one of the Х Tier 2 treatment groups) Х Any Grade 3 to 5 AE (\geq 5% of participants in one of the treatment groups) AEs, Specific AEs, SOCs

Table 4 **Analysis Strategy for Safety Parameters**

	Discontinuation due to AE		Х
Tier 3	Dose interruption due to AE		Х
	Change from baseline results (laboratory, ECGs, Vital Signs)		Х
Abbreviations: SOC = system organ class; X = results will be provided			

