MK-6482-001 (PT2977-101) is an ongoing Phase 1 study designed to assess the tolerability, safety, PK, and pharmacodynamic properties of belzutifan in participants with various advanced solid tumors. As of 06-SEP-2019 a total of 104 participants had been enrolled, including 43 participants with various advanced solid tumors in the dose-escalation portion (Part 1A) ranging from 20 to 240 mg QD and 120 mg BID. The MTD was not reached and 2 treatment-related DLTs were observed, 1 Grade 4 event of thrombocytopenia in the 240 mg QD cohort, and 1 Grade 3 event of hypoxia in the 120 mg BID cohort. The 120 mg QD dose was selected for further clinical development based on favorable PK, pharmacodynamic, and safety findings. 52 additional participants with advanced RCC were treated in an expansion cohort (Part 1B) at the clinical dose of 120 mg QD. In the combined dose escalation and expansion cohorts, the most common AEs (occurring in $\geq 20\%$ of participants) were anemia, fatigue, dyspnea, nausea, and peripheral edema. The most common Grade 3 AEs were anemia and hypoxia (in \geq 5% of participants). The median t_{max} for belzutifan was 1 to 2.8 hours and exposure increased with dose. The mean steady state t1/2 in the 120 mg QD expansion cohort (Part 1B) on Day 15 was 15.4 hours, resulting in a 1.5-fold accumulation from Day 1 to Day 15. The mean steady state C_{max} in the 120 mg QD expansion cohort (Part 1B) on Day 15 was 1.79 μ g/mL (4.67 μ M). The estimated CL/F was 5.22 to 14.4 L/h. The estimated Vz/F was 106 to 266 L, which suggests extensive distribution to peripheral tissues. The CV was 32 to 59% for C_{max} and 24 to 48% for AUC after a single dose, and 27 to 56% for C_{max} and 30 to 64% for AUC at steady state. In total, 55 participants with previously treated advanced RCC have been treated in this study with belzutifan at 120 mg QD (3) participants in the dose-escalation portion of the study and 52 participants in the dose expansion portion of the study). Best response among these 55 participants included 11 participants (20%) with PR and 32 participants (58%) with SD as assessed by RECIST v1.1.

During the dose-escalation portion of the MK-6482-001 (PT2977-101) study, the dose of 120 mg BID was well tolerated in the 6-participant cohort with only 1 DLT of Grade 3 hypoxia observed. The BID dosing regimen had a higher steady state plasma exposure compared with other dose levels.

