6.6.1 Belzutifan Dosing Modifications

Guidelines for dose modification for belzutifan are listed in Table 3. Specific dose reduction levels are listed in Table 4.

The following should be considered in decisions regarding dose modifications:

- As a general approach, all AEs should be managed with supportive care at the earliest signs of toxicity considered related to belzutifan treatment. Should this be ineffective, dose reductions or interruptions should be considered to prevent worsening of toxicity.
- Dose reductions and/or interruptions, at any time while on study, should be implemented for unacceptable toxicity.
- Dose modifications or interruptions may also occur in the setting of lower grade toxicity than defined in Table 3, if the investigator feels it is in the interest of a participant's safety and will optimize drug tolerability.
- Interruption of belzutifan treatment for AEs may occur at any time per investigator discretion. An interruption of study treatment for >28 days will require Sponsor consultation.

The AE profile of belzutifan indicates that anemia and hypoxia have been associated with belzutifan treatment. Guidelines for the management of anemia and hypoxia are provided in Section 6.6.1.1 and Section 6.6.1.2, respectively. ECIs for belzutifan and guidelines for reporting these AEs as ECIs are provided in Section 8.4.7. Refer to the ECI Guidance (Appendix 8) for additional practice guidelines and management recommendations for AEs potentially related to belzutifan treatment.

Belzutifa	an-related Toxicity	Action			
Anemia	• Grade 4 anemia	 First episode: Hold belzutifan. Once toxicity has resolved to ≤Grade 2 or baseline, dose reduce belzutifan by one level. Second episode: Permanently discontinue belzutifan. 			
Neutropenia/Febrile neutropenia	 Grade 3 febrile neutropenia (ANC <1000/mm3 with a single temperature of >38.3 degrees C (101 degrees F) or a sustained temperature of >=38 degrees C (100.4 degrees F) for more than one hour,) or Grade 4 neutropenia for >5 days 	 First and second episodes: Hold belzutifan. Once toxicity has resolved to ≤Grade 2 or baseline, dose reduce belzutifan by one level. Third episode: Permanently discontinue belzutifan. 			
	• Grade 4 febrile neutropenia	• Permanently discontinue belzutifan.			

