8.4.7 Events of Clinical Interest

Selected nonserious and SAEs are also known as ECIs and must be reported to the Sponsor. ECIs that are not SAEs should be collected through 30 days following cessation of study intervention and must be reported by the investigator. ECIs that are SAEs should be collected through 90 following cessation of study intervention and must be reported by the investigator.

Events of clinical interest for this study include:

- a. An overdose of Sponsor's product, as defined in Section 8.5.
- b. Potential DILI events defined as an elevated AST or ALT laboratory value that is greater than or equal to 3X the upper limit of normal and an elevated total bilirubin laboratory value that is greater than or equal to 2X the upper limit of normal and, at the same time, an alkaline phosphatase laboratory value that is less than 2X the upper limit of normal, as determined by way of protocol-specified laboratory testing or unscheduled laboratory testing.*

*Note: These criteria are based upon available regulatory guidance documents. The purpose of the criteria is to specify a threshold of abnormal hepatic tests that may require an additional evaluation for an underlying etiology. The study site guidance for assessment and follow-up of these criteria can be found in the Investigator Study File Binder (or equivalent).

- c. Any ≥Grade 3 anemia
- d. Any ≥Grade 3 hypoxia
- e. Any ≥Grade 3 AE deemed related to belzutifan by the investigator, including laboratory abnormalities

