10.8 Appendix 8: Belzutifan ECI Guidance

10.8.1 Belzutifan ECI Criteria

Anemia: Any ≥ Grade 3 anemia/decreased hemoglobin event				
Anemia Decreased hemoglobin				
Hypoxia: Any ≥ Grade 3 hypoxia				
Нурохіа				
Any ≥Grade 3 SAE/AE deemed related to belzutifan by the investigator, including laboratory				
abnormalities.				
\geq Grade 3 belzutifan-related clinical AEs \geq Grade 3 belzutifan-related laboratory AEs				
Common Terminology Criteria for Adverse Events (CTCAE) Version 5 will be used.				

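### A between-arm confidence interval is not guaranteed for the pre-declared events of clinical interest (Grade 3 or higher hypoxia and anemia), because it depends on an observed frequency cut-off

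*SAP*

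**What the plan says.** Protocol 8.4.7 lists "Any ≥Grade 3 anemia" and "Any ≥Grade 3 hypoxia" among the events of clinical interest. Appendix 8 (10.8.1) repeats them and defines the first as an "anemia/decreased hemoglobin event", so two terms form one ECI. Protocol 6.6.1 gives the reason for the interest: "The AE profile of belzutifan indicates that anemia and hypoxia have been associated with belzutifan treatment".

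SAP 3.6.2 sets up three safety tiers.

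- **Tier 1.** "Safety parameters or adverse events of special interest that are identified a priori constitute Tier 1 safety endpoints", and these would be formally tested. The SAP then says that no adverse event is known for which a p-value would affect the safety assessment: "Therefore, there are no Tier 1 events for this protocol".
- **Tier 2.** These events get a Miettinen and Nurminen difference with a 95% CI. "Membership in Tier 2 requires that at least 10% of participants in any treatment group exhibit the event". Grade 3 to 5 events and serious events also qualify, each at 5% or more in one arm. Protocol 9.6.2 has the same rule.
- **Tier 3.** Everything else gets a point estimate for each arm and no interval for the difference.

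Neither section gives the ECIs an analysis of their own. On expected rates, Protocol 2.2.6 says of Phase 1 that "The most common Grade 3 AEs were anemia and hypoxia", each in 5% or more of participants, and lists anemia, but not hypoxia, among events of any grade seen in 20% or more.

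**The concern.** Comparing safety with everolimus is a stated secondary objective, and anemia and hypoxia are the two toxicities that the protocol itself attributes to belzutifan. Whether the report shows a difference and interval for them is left to the observed data. The SAP's reason for a frequency filter is that rarer events would obscure the overall picture. That suits unselected adverse events; it does not suit two events named in advance.

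The tiers also work on specific terms and system organ class terms, while Appendix 8 treats anemia and decreased hemoglobin as one event. If both terms are used in coding, each must pass the cut-off by itself, and no table gives the number of participants with either.

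**Working it through.** **Check of the sample size.** The plan states no operating figure for the tiers, so the per-arm size was checked against the ORR power. Inputs: 368 per arm (Protocol 4.1), 5% vs 20%, one-sided alpha 0.001 (SAP 3.9). With mean rate 0.125:

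- SE under the null = √(2 × 0.125 × 0.875 / 368) = 0.02438
- SE under the alternative = √((0.05 × 0.95 + 0.20 × 0.80) / 368) = 0.02375
- Power = Φ((0.15 − 3.090 × 0.02438) / 0.02375) = Φ(3.14) = 99.92%, against the stated 99.9%.

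**Cut-offs in participants.** It is assumed that all 368 in the arm are treated.

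- 5%: 0.05 × 368 = 18.4, so 19 are needed.
- 10%: 0.10 × 368 = 36.8, so 37 are needed.

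**Chance of reaching a cut-off in one arm.** P(X ≥ c) with X ~ Binomial(368, p).

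| Route | True rate | Probability |
|---|---|---|
| Grade 3 to 5, c = 19 | 3% | 1.7% |
| | 4% | 15.7% |
| | 5% | 47.6% |
| | 6% | 78.0% |
| | 7% | 93.6% |
| | 8% | 98.7% |
| Any grade, c = 37 | 8% | 9.1% |
| | 9% | 26.4% |
| | 10% | 51.2% |
| | 11% | 74.2% |
| | 12% | 89.3% |
| | 15% | 99.8% |

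At a true Grade 3 or higher rate of 5%, arm sizes of 350, 360 and 364 give 48.5%, 53.4% and 45.7%, so the result does not hinge on 368.

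**Two routes together for hypoxia.** Simulation, 200,000 draws per cell, chance that either the Grade 3 to 5 or the any-grade cut-off is met. The any-grade rates are assumptions, since the documents give none.

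| Grade 3+ rate | Any grade 8% | 10% | 12% | 15% |
|---|---|---|---|---|
| 3% | 9.7% | 51.4% | 89.2% | 99.8% |
| 5% | 48.0% | 62.2% | 90.0% | 99.8% |
| 8% | 98.7% | 98.7% | 98.9% | 99.9% |

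Serious events and the everolimus arm were not modelled. Either could also bring the event into Tier 2, so both can only raise these values.

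**What Phase 1 supports.** A rate of 5% or more is a floor. The smallest counts that satisfy it in the Phase 1 groups of Protocol 2.2.6 are 3/52, 3/55, 5/95 (43 + 52) and 6/104. A beta-binomial prediction with a Jeffreys prior from these gives 56% to 63% for the Grade 3 to 5 route; one more event in each gives 70% to 80%.

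**Anemia.** At the 20% any-grade floor, P(X ≥ 37) exceeds 99.99%. An interval for Grade 3 or higher anemia is still subject to the 5% cut-off.

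**The case against.** The strongest reply is that little is lost. Tier 3 still reports each arm's rate, so with about 368 per arm a reader can calculate the difference and interval for a single term. The SAP calls the Tier 2 intervals descriptive, no decision rule uses them, and the DMC reviews safety separately. The cut-offs are prespecified with a rationale. All of this stands, and it limits the point to a minor one. It does not cover a pooled anemia rate: a participant may have both terms, so the pooled count cannot be rebuilt from separate rows.

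Some stronger readings are tempting but not supported.

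- *A reader might infer that a comparison for hypoxia is a coin flip.* The Grade 3 to 5 route gives 40% to 60% only for true rates of about 4.8% to 5.35%, and only while any-grade hypoxia stays at or below about 10%. The documents give a floor, drawn from pooled doses. The rate here could be well above 5%, or below it: the only Grade 3 or higher event that Protocol 2.2.6 names for the VHL study is fatigue.
- *A reader might infer that the anemia comparison could be absent.* For any-grade anemia that is practically excluded.
- *A reader might infer that the empty Tier 1 contradicts the ECI list.* Tier 1 is for formal testing, and the SAP says why it is empty. ECIs are a reporting class that also includes overdose and potential liver injury, and nothing in the documents says that ECI status requires a test.
- *A reader might infer that splitting anemia over two terms understates its rate.* It may, but the documents do not describe the coding. Appendix 3 asks investigators to record the diagnosis and not its signs, which favours one term.

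The SAP (November 2022) also predates Appendix 8, which came with protocol amendment 09. This explains the gap but does not close it, because Protocol 9.6.2 in the current version has the same rule.

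**Conclusion.** The plan does not guarantee a between-arm 95% CI for either pre-declared ECI, and it defines no pooled ECI endpoint. For Grade 3 or higher hypoxia, the chance of reaching Tier 2 on the Grade 3 to 5 route runs from about 2% at a true rate of 3% to about 99% at 8%, and other routes can only add to it. Where this trial falls in that range cannot be settled from the documents. For anemia, an any-grade interval is practically certain; what remains open is the Grade 3 or higher ECI and its pooling with decreased hemoglobin, whose effect cannot be sized without the coding rules.

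The figures assume about 368 treated participants per arm and independent participants with a common rate. Severity is minor: the intervals are descriptive, and most of what is missing could be derived from the reported counts.

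**What to change.** In Protocol Table 9 and SAP Table 4, add one fixed Tier 2 row with two entries: ECI anemia, counting each participant with anemia or decreased hemoglobin once, and ECI hypoxia. Show each for any grade and for Grade 3 to 5, with the Miettinen and Nurminen difference and 95% CI whatever the observed incidence, and label the row descriptive. State in Protocol 9.6.2 and SAP 3.6.2 that these entries are exempt from the frequency cut-offs.

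The cost is one table row and one output. It needs no new data, no alpha and no change to Tier 1, and it uses the method that the plan already has.

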3.6.3 Statistical Methods for Patient-Reported Outcomes (PRO) Analyses

This section describes the planned analyses for the PRO endpoints.

3.6.3.1 PRO Scoring Algorithm

QLQ-C30 Scoring

The QLQ-C30 is composed of both multi-item scales and single-item measures. These include a global health status / QoL scale, five functional scales, three symptom scales, and six single

items. Each of the multi-item scales includes a different set of items - no item occurs in more than one scale.

All of the scales and single-item measures will follow a standardization procedure prior to analysis so that scores range from 0 to 100. A high scale score represents a higher response level. Thus a high score for a functional scale represents a high / healthy level of functioning; a high score for the global health status / QoL represents a high QoL; but a high score for a symptom scale / item represents a high level of symptomatology / problems.

According to the EORTC QLQ-C30 Scoring Manual [9], the principle for scoring these scales is the same in all cases:

1. Estimate the average of the items that contribute to the scale; this is the raw score.

2. Use a linear transformation to standardize the raw score, so that scores range from 0 to 100; a higher score represents a higher ("better") level of functioning, or a higher ("worse") level of symptoms.

Specifically, if items $I_1, I_2, ..., I_n$ are included in a scale, the scoring procedure is as follows:

1. Compute the raw score: $RS = (I_1 + I_2 + ... + I_n)/n$

2. Linear transformation to obtain the score *S*:

Function scales: $S = \left(1 - \frac{RS - 1}{Range}\right) \times 100$

Symptom scales / items: $S = \frac{RS - 1}{Range} \times 100$

Global health status / QoL:
$$S = \frac{RS - 1}{Range} \times 100$$

Range is the difference between the maximum possible value of *RS* and the minimum possible value. The QLQ-C30 has been designed so that all items in any scale take the same range of values. Therefore, the range of *RS* equals the range of the item values. If more than half of the items within one scale are missing, then the scale is considered missing, otherwise, the score will be calculated as the average score of those available items.

EQ-5D-5L Scoring

The EQ-5D-5L utility score will be calculated based on the European algorithm [10] based on responses on the five health state dimensions, including mobility, self-care, usual activities, pain / discomfort, and anxiety / depression. The EQ-5D also includes a graded (0 to 100) vertical visual analog scale (VAS) on which the participant rates his or her general state of health at the time of the assessment.

FKSI-DRS scoring

The FKSI-DRS includes 9 questions which are negatively stated items [6]. So the score for each item must be reversed by subtracting the response from "4". After that, all the item scores are summed to a total, which is the subscale score. The final FKSI-DRS score is defined as below.

Higher scores correspond with better QoL.

FKSI-DRS score = Subscale score \times 9 \div Number of items answered

Such FKSI-DRS score is a prorated score if there are missing items. It is acceptable as long as more than 50% of the items were answered (e.g., a minimum of 5 of 9 items). Otherwise, the FKSI-DRS score is considered as missing.

3.6.3.2 PRO completion and compliance summary

Completion and compliance of EORTC QLQ-C30, FKSI-DRS, and EQ-5D VAS by visit and by treatment will be described. Numbers and percentages of complete and missing data at each visit will be summarized.

Completion rate of treated participants (CR-T) at a specific visit for a given instrument is defined as the number of treated participants who complete at least one item on that PRO instrument over the number of treated participants in the PRO analysis population.

 $CR-T = \frac{Number of treated participants who complete at least one item}{Number of treated participants in the PRO analysis population}$

The completion rate is expected to decrease at later visits during study period for reasons such as study design (e.g., PROs not required following progression), patient discontinuation, etc. Therefore, the compliance rate (CR-E) will also be presented in addition to completion rate. CR-E is defined as the number of treated participants who complete at least one item of the instrument over number of participants who are expected to complete the PRO assessment at that visit, excluding participants missing by design such as death, discontinuation, translation not available.

$$CR-E = \frac{Number of treated participants who complete at least one item}{Number of treated participants who are expected to complete}$$

The completion and compliance status will be summarized as below:

- Completed as scheduled
- Not completed as scheduled
- Off-study: not scheduled to be completed.

The reasons for non-completion as scheduled of these measures are collected using "miss_mode" forms filled by site personnel and will be summarized in a table format. The

schedule (study visits and estimated study times) and mapping of study visit to analysis visit for PRO data collection is provided in Table 5 and Table 6.

Study Period	Screening	r	Freatme	nt Period		ЕОТ	Posttreatment		
Visit:	Screening ^a	Wk 1 Day 1 ^a	Wk 3 Day 1	Wk 5 Day 1	Wk 9 Day 1	Wk 13+ Day 1 ^b	DC	Safety Follow-up	
Scheduling Window (Days):	-28 to -1	+3	±3	±3	±3	±5	At time of DC	30 Days After Last Dose (+7 days)	
Patient-reported Outcomes									
FKSI-DRS		Х	Х	Х	Х	Q4W	Х	Х	
EORTC QLQ- C30		Х	Х	Х	Х	Q4W	Х	Х	
EuroQoL EQ- 5D-5L		Х	X	Х	Х	Q4W	Х	Х	
a. Week 1 Day 1 denotes the first dose of study treatment, which should be on the date of randomization, but can be within 3 days following randomization. Every effort should be made to ensure the participants receive the first dose of study intervention on the day of randomization.									

Table 5PRO Data Collection Schedule

b. Clinic visits after Week 13 are Q4W.

Treatment Week	1	3	5	9	13	17	21	25	29	33
Target Day ^a	1	15	29	57	85	113	141	169	197	225
Range ^a	-28 - 1	2 - 22	23 - 43	44 - 71	72 - 99	100 - 127	128 - 155	156 - 183	184 - 211	212 - 239
Treatment Week	37	41	45	49	53	57	61	65	69	73
Target Day ^a	253	281	309	337	365	393	421	449	477	505
Range ^a	240 - 267	268 - 295	296 - 323	324 - 351	352 - 379	380 - 407	408 - 435	436 - 463	464 - 491	492 - 519
Treatment Week	77	81	85	89	93	97	101	105	109	113
Target Day ^a	533	561	589	617	645	673	701	729	757	785
Range ^a	520 - 547	548 - 575	576 - 603	604 - 631	632 - 659	660 - 687	688 - 715	716 - 743	744 - 771	772 - 799
Treatment Week	117	121	125	129	133	137	141	145	149	153
Target Day ^a	813	841	869	897	925	953	981	1009	1037	1065
Range ^a	800 - 827	828 - 855	856 - 883	884 - 911	912 - 939	940 - 967	968 - 995	996 - 1023	1024 - 1051	1052 - 1079
Treatment Week	157	161	165	169	173	177	181	185	189	193
Target Day ^a	1093	1121	1149	1177	1205	1233	1261	1289	1317	1345
Range ^a	1080 - 1107	1108 - 1135	1136 - 1163	1164 - 1191	1192 - 1219	1220 - 1247	1248 - 1275	1276 - 1303	1304 - 1331	1332 - 1359
a. Day = Date	of the assess	sment – date	of the first d	ose +1						

Table 6Mapping of Study visit to Analysis Visit

